A placebo arm is included in this study design in order to robustly demonstrate the safety and efficacy of E-WE thrombin while not placing the patients at unnecessary risk, as mentioned above. The primary endpoint in this study is safety, measured as the number or frequency/rate of AEs that occur during the comparable observation periods. A heparin-free inpatient HD observation period (from Day -8 to Day 1 prior to dosing) is included in the trial design to establish a baseline for the heparin-free procedure. Continuation of the heparin-free HD procedure during the subsequent trial period and inclusion of a placebo arm allows for the determination of whether an AE is drug-related or not and permits accurate assessment of the safety of the study drug. The addition of a placebo arm also removes potential bias from the interpretation of AEs by the PIs and from the reporting by the patients. The secondary endpoint for this study is efficacy of E-WE thrombin on HD which may be more clearly observed with a placebo control instead of an active control (e.g., heparin). While the placebo arm may be at the same risk of clotting within the dialysis circuit as during the pre-dosing period (Days -8 to 1), data cited above suggests that these patients will not be at higher risk for either thromboembolic or bleeding complications. Should clotting occur within the dialyzer cartridge during a HD session that results in dialyzer failure, the dialyzer cartridge will be replaced, and the patient will be closely monitored by

the PI. It is important to note that replacement of the dialyzer cartridge during HD is safe for the patient and a routine procedure in cases of dialyzer failure.

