9.2 Study Endpoints

Primary outcome measures:

- The safety and tolerability of E-WE thrombin following active treatment will be evaluated versus pre-treatment and placebo by number and severity of AEs (including HD vascular access site reactions), physical examinations, bleeding time from the HD vascular access sites, vital sign measurements, 12-lead ECGs, clinical laboratory tests, and coagulation tests.

Secondary outcome measures:

- PD of E-WE thrombin will be measured by APC-PCI and plasma APC-PCI will act as a surrogate marker for E-WE thrombin drug exposure.
- Efficacy of antithrombotic activity will be evaluated by thrombus accumulation within the dialyzer cartridge (evaluated by visual inspection) after E-WE thrombin active treatment versus pre-treatment and placebo.
- Efficiency of HD will be assessed using BUN levels before and after dialysis to determine urea removed by 4 hours of dialysis (Kt/V and URR) after E-WE thrombin active treatment versus pre-treatment and placebo.

Other outcome measures:

- Development of antibodies to E-WE thrombin or WT thrombin after drug exposure.

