13.2.8.3 Reporting

All AEs that occurred during this clinical study (i.e., before, during, and after exposure of ESRD patients to E-WE thrombin) will be recorded. This design is to improve Sponsor ability to obtain reliable initial information about drug safety yet reducing the number of study patients needed to generate useful information.

AEs and SAEs, including those related to study participation (e.g., protocol-mandated intervention), will be recorded from the time of patient check-in until study completion.

AEs will be coded using the most current Medical Dictionary for Regulatory Activities (MedDRA)[®] available at Celerion.

The PI or designee will review each event and assess its relationship to study drug (likely, probably, possibly, unlikely, or unrelated) and severity. The date and time of onset, time relationship to drug dosing, duration, and outcome of each event will be noted.

Relationship of AE:

The relationship of each AE to the study drug will be assessed using the following definitions:

Unrelated	
 ▪ The adverse event must clearly be caused by the participant's clinical state, or the study procedure/conditions ▪ Definitely not related to drug ▪ Temporal sequence of an adverse event onset relative to administration of drug not reasonable ▪ Another obvious cause of an adverse event
Unlikely	
 ▪ Time sequence is unreasonable ▪ There is another more likely cause for an adverse event
Possibly	
 ▪ Corresponds to what is known about the drug ▪ Time sequence is reasonable ▪ Could have been due to another equally, likely cause
Probably	
 ▪ Is a known effect of the drug ▪ Time sequence from taking drug is reasonable ▪ Ceases on stopping the drug ▪ Cannot be reasonably explained by the known characteristics of the participant's clinical state
Likely	
 ▪ Is a known effect of the drug (e.g. listed in IB) ▪ Time sequence from administering drug is reasonable ▪ Event stops upon stopping drug and returns upon restarting drug

Severity of AE:

Severity rating used during the study will be based on the toxicity grading scale tables present in the FDA (Center for Biologics Evaluation and Research) toxicity grading scale for healthy volunteers 4-point severity scale (Grade 1, 2, 3 and 4) [11].

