14.3.1 Safety and Tolerability Analyses

All safety data will be populated in the individual CRFs. All safety data will be listed by patients.

The placebo patients from all cohorts will be pooled into a single placebo group for all summaries and presentations.

Dosing dates and times will be listed by patient.

Incidence and time of bleeding from the HD access sites on the AV fistula (or AV graft), as described in [Section 13.2.6](#), will be counted and recorded. Active treatment versus pre-treatment, placebo, and post-treatment results will be compared.

AEs will be coded using the most current version of Medical Dictionary for Regulatory Activities (MedDRA®) available at Celerion and summarized by treatment (2 active dose levels and pooled placebo) for the number of patients reporting the treatment emergent adverse event (TEAE) and the number of TEAEs reported. A by-patient AE data listing including verbatim term, coded term, treatment, severity, and relationship to study drug will be provided.

Safety data including ECGs, vital signs assessments, clinical laboratory results, and vascular access site reaction will be summarized by treatment (2 active dose levels and pooled placebo) and point of time of collection.

Descriptive statistics using appropriate summary statistics will be calculated for quantitative safety data as well as for the difference to baseline, when appropriate. In addition, a shift table describing out of normal range shifts will be provided for clinical laboratory results.

Concomitant medications will be listed by patient and treatment (2 active dose levels and pooled placebo) and coded using the most current version of the World Health Organization drug dictionary available at Celerion. Medical history will be listed by patient.

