2.2 Endpoints

Primary outcome measures:

- The safety and tolerability of E-WE thrombin following administration of the active treatment will be evaluated versus pre-treatment and placebo by number and severity of AEs (including HD vascular access site reactions), physical examinations, bleeding time from the HD vascular access sites, vital sign measurements, 12-lead ECGs, clinical laboratory tests, and coagulation tests.

Secondary outcome measures:

- Pharmacodynamics of E-WE thrombin will be measured by APC-PCI and plasma APC-PCI will act as a surrogate marker for E-WE thrombin drug exposure.
- Efficacy of antithrombotic activity will be evaluated by thrombus accumulation within the dialyzer cartridge (evaluated by visual inspection) after E-WE thrombin active treatment versus pre-treatment and placebo.
- Efficiency of HD will be assessed using BUN levels before and after dialysis to determine urea removed by 4 hours of dialysis (Kt/V and URR) after E-WE thrombin active treatment versus pre-treatment and placebo.

Other outcome measures:

- Development of antibodies to E-WE thrombin or WT thrombin after drug exposure.

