7.3 Adverse Events

All adverse events (AEs) occurring during this clinical trial will be coded using the Medical Dictionary for Regulatory Activities (MedDRA®), Version 21.1.

All AEs captured in the database will be listed in by-subject data listings including verbatim term, coded term, treatment, severity, relationship to study medication, and action; however, only treatment-emergent AEs (TEAEs) will be summarized.

A TEAE is defined as an AE that is starting or worsening at the time of or after study drug administration. Each TEAE will be attributed to a treatment based on the onset date and time of the AE. If the onset time of an AE is missing and the onset date is the same as the treatment dosing date, then the AE will be considered treatment emergent. If the onset date of an AE is missing, then the AE will be considered treatment emergent.

TEAEs will be tabulated by System Organ Class (SOC) and Preferred Term. Summary tables will include number of subjects reporting the AE and as percent of number of subjects dosed by treatment and overall. The number of AEs will be tabulated in a similar manner. Tables which tabulate the number of TEAEs by severity and relationship to study treatment will also be included.

Serious adverse events (SAEs), if present, will also be listed. Applicable narratives will be included in the CSR.

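### The primary AE outcome is to be compared with pre-treatment, but no planned AE frequency table has a pre-treatment period

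*SAP*

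**What the plan says.** **The outcome.** Protocol 9.2 states that safety "following active treatment will be evaluated versus pre-treatment and placebo by number and severity of AEs". SAP 2.2 repeats that it "will be evaluated versus pre-treatment and placebo by number and severity of AEs".

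**The source of the pre-treatment data.** Protocol 8.3.1 says that the heparin-free inpatient period before dosing "is included in the trial design to establish a baseline for the heparin-free procedure". It also describes the primary endpoint as a count or rate of AEs over comparable periods. Under Protocol 13.2.8.3, AEs "will be recorded from the time of patient check-in until study completion". Protocol 13.2.8.2 has patients questioned once a day in confinement and again at follow-up.

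**The planned analysis.** Protocol 14.3.1 summarises AEs by treatment "for the number of patients reporting the treatment emergent adverse event (TEAE) and the number of TEAEs reported". For access-site bleeding, the same section keeps the comparison with the run-in: "Active treatment versus pre-treatment, placebo, and post-treatment results will be compared". It also plans a summary of access-site reactions by treatment and time of collection.

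SAP 7.3 lists every AE, but "only treatment-emergent AEs (TEAEs) will be summarized". A TEAE is one that starts or worsens at or after dosing. "If the onset date of an AE is missing, then the AE will be considered treatment emergent"; the same applies to a Day 1 onset with no recorded time. SAP section 8 reports no departure from the protocol.

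**The concern.** The comparator named in the endpoint does not reach the analysis. Each document contradicts itself: Protocol 9.2 against 14.3.1, and SAP 2.2 against 7.3.

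The run-in AEs matter to the design. Protocol 8.3.1 relies on the run-in together with placebo to judge whether an AE is drug-related. Protocol 13.2.8.3 defends recording AEs before, during and after exposure as a way to learn more from fewer patients.

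If the plan is followed exactly, the report will contain no count, severity breakdown or rate of run-in AEs. A reader would have to build the comparison from by-patient listings, over periods of different length and different intensity of questioning. Raw counts taken that way could mislead.

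**Working it through.** The plan gives no figure to reproduce, and Protocol 14.1 says that the sample size has no statistical basis. The check compares the planned displays with the endpoint and then sizes the gap from the schedule.

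**1. Displays.**

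| Display | Content | Pre-treatment period shown? |
|---|---|---|
| Table 12-1 | TEAE rows, sourced from 14.3.1.1 | No |
| Table 14.3.1.1 | Patients with TEAEs | No |
| Table 14.3.1.2 | Number of TEAEs | No |
| Table 14.3.1.3 | TEAEs by severity and relationship | No |
| Table 14.3.2.1 | Listing of serious AEs | Not limited to TEAEs by title, but no counts by period |
| Appendices 16.2.7.1.1, 16.2.7.1.2, 16.2.7.2 | By-patient AE listings; 16.2.7.1.1 and 16.2.7.2 carry a treatment-emergent flag | Events listed, no counts |

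None of the four frequency tables shows a pre-treatment period.

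**2. Which run-in AEs can reach a frequency table.** There are three routes: the AE worsens after dosing, its onset date is missing, or its onset is on Day 1 before dosing with no time recorded. In each case it is counted as treatment-emergent and not as a pre-treatment event.

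**3. Access-site reactions.** Protocol 14.3.1 would summarise them by time point. The flow chart and SAP 7.10 schedule the assessment at Day 1 predose, at the end of the Day 1 session, and before and after the Day 3 session. SAP 7.10 summarises new findings only as AEs and lists the rest, and SAP 9.2 has no table by time point. The protocol's predose summary is therefore not carried through.

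**4. Length of the periods.** Protocol 10.1 puts Day -8 eight days before Day 1, so there is no Day 0. Follow-up is Day 14 ± 2.

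- Before dosing: 8 days.
- After dosing: 14 − 1 = 13 days (12 − 1 = 11 to 16 − 1 = 15), made up of 2 confined days (Day 1 to Day 3) and 11 (9 to 13) after discharge.
- Share of observed days with no AE summary: 8/(8 + 13) = 38%; range 8/23 = 35% to 8/19 = 42%.
- Dialysis sessions before dosing: Days -7, -5 and -2, so 3/5 = 60%, or 108 of 180 sessions if all 36 patients are dosed and complete.
- Daily questioning: Days -8 to -1 give 8 occasions and Days 1, 2 and 3 give 3, so 8/11 = 73% fall before dosing, assuming that the Day 1 question follows dosing (9/11 = 82% if it precedes dosing).

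**5. Why raw counts would mislead.** At a constant event rate and equal ascertainment, the post-dose count would be 13/8 = 1.63 times the pre-dose count (11/8 = 1.38 to 15/8 = 1.88) with no drug effect.

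**6. Patient-days per group of 12** (each active arm, and pooled placebo), assuming full follow-up.

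- Before dosing: 12 × 8 = 96.
- After dosing, confined: 12 × 2 = 24.
- After discharge: 12 × 11 = 132 (108 to 156).
- All post-dose: 24 + 132 = 156 (132 to 180).

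With zero events, the one-sided 95% Poisson upper bound is −ln(0.05) = 2.996 divided by patient-days. That gives 2.996/96 = 0.031 per patient-day before dosing, 2.996/156 = 0.019 over all post-dose time, and 2.996/24 = 0.125 if only confined post-dose time is used. Any such comparison is descriptive.

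**The case against.** Restricting AE summaries to TEAEs is conventional, and the randomised placebo group is the better comparator. Every AE in a dosed patient is still listed with onset and severity, so with 12 patients per group the pre-treatment count can be rebuilt by hand. All of this is true, and it keeps the point modest. It does not remove the conflict: both documents name pre-treatment as a comparator for AEs, and a listing gives neither counts nor rates.

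The missing-date rule is also defensible. It applies equally to all groups, Protocol 13.2.8.3 requires onset date and time to be noted, and nothing suggests that undated AEs will be common. In the planned TEAE tables each such event adds 1. Only in a before/after table would a misplaced run-in event shift the difference by 2 (one fewer before, one more after).

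A reader might infer three stronger claims that the documents do not support:

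- **That no run-in AE can ever appear in an AE table.** Step 2 of the working shows three routes by which one can.
- **That the whole primary outcome lacks a comparison with pre-treatment.** Bleeding time, coagulation tests, platelet count and vital signs are tabulated on run-in days (SAP 7.4, 7.5, 7.11 and the Table 14.3.5 shells). The gap is in the AE component.
- **That the drug-versus-placebo comparison is compromised.** TEAEs are defined and counted in the same way in all groups.

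**Conclusion.** The point holds for the AE component of the primary outcome. One of its two stated comparisons has no planned summary, and SAP section 8 does not disclose this. A linked and smaller gap is that the access-site reaction summary by time point in Protocol 14.3.1 is missing from the SAP.

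The size is best read as coverage: about 38% of observed days and 60% of dialysis sessions per dosed patient have no AE summary. No bias in a treatment effect is implied. The figures assume the scheduled days, dosing of all 36 patients for the session total, and complete follow-up for the patient-days. The before/after comparison would be imprecise and unequal in ascertainment, so it should be presented as descriptive.

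**What to change.** In SAP 7.3 and 9.2, and in Protocol 14.3.1 at the next amendment, add one descriptive table of AEs (patients, events, severity) by treatment and period, with boundaries that do not overlap:

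1. check-in to start of dosing;
2. start of dosing to discharge on Day 3, including the Day 3 dialysis session;
3. discharge to follow-up.

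Give patient-days and events per patient-day, and footnote that daily questioning applies only in confinement. In this table only, show AEs whose onset cannot be placed before or after dosing in a separate row. The TEAE rule stays as it is elsewhere.

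Also add the access-site reaction summary by time point that Protocol 14.3.1 already plans, noting that the scheduled assessment begins only at Day 1 predose and so does not cover the run-in.

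If the sponsor does not intend a pre-treatment comparison for AEs, amend Protocol 9.2 and SAP 2.2 instead. Under Protocol 14.3, a major change to the definition of a primary endpoint must appear in a protocol amendment, so this route is not necessarily simpler.

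The cost is one extra AE table, the access-site summary and a sentence in each document. The data are already collected. The new table's post-dose count may differ from the TEAE tables by any undated events, which needs a footnote. The protocol change needs sponsor, investigator and IRB approval (Protocol 15.8), which is why it can wait for the next amendment.

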E-WE thrombin is expected to reduce thrombogenesis by downregulating thrombin generation in the extracorporeal circuit and hemodialyzer without clinically significant impairment of the patient's hemostasis or promoting thrombosis. Both thromboembolism and bleeding are common comorbidities in ESRD patients on HD, and heparin for HD is not well tolerated in some patients, as about 4% of ESRD patients develop heparin-induced thrombocytopenia (HIT). Severe HIT is a life-threatening acute complication of heparin exposure. HIT antibodies have been detected in about 8% of HD patients who receive unfractionated heparin, and some of them are at risk of developing a severe HIT event. Thus, an intrinsically safe short-term and self-limiting anticoagulant as an alternative to heparin is currently an unmet need for this patient population. As such, E-WE thrombin administration during HD may be an effective method to protect the hemodialyzer from clot development, and stands as a promising, short-acting alternative to other anticoagulants in this population. It is therefore of interest to assess E-WE thrombin safety and effectiveness in ESRD patients on chronic HD.

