8.4 Risk/Benefit

ESRD patients are often ill and are prone to a variety of AEs on or off HD, ranging, for example, from infections to hypertension to bleeding to thromboembolism to acute ischemic cardiovascular emergencies, even if they are apparently stable on chronic HD.

E-WE thrombin is a purified protein produced by recombinant DNA technology in a bacterial (*Escherichia coli*) cell culture system. All drugs, including heparins or recombinant proteins can occasionally and unpredictably evoke acute or chronic allergic reactions. Some ESRD patients develop chronic HD- and uremia-related moderate hemorrhagic diathesis or hemostasis impairment. The hemostatic safety of E-WE thrombin in the complex conditions of ESRD and chronic HD is not yet known. The safety monitoring practices employed by this protocol (i.e., AE questioning [including HD vascular access site reaction], physical examinations, bleeding time from the HD vascular access sites, vital sign measurements, 12-lead ECGs, clinical laboratory and coagulation tests) are adequate to protect the patients' safety and should detect all expected and unexpected TEAEs. In addition, the cohorts will be dosed in a sequential manner, starting with the lower dose level, Cohort 1.

There may be a higher risk of clots developing in the hemodialyzer during heparin-free HD. Should this occur, the site standard operating procedures will be followed to replace the clotted dialyzer and resume HD using a new cartridge under the supervision of the PI. It is important to note that replacement of the dialyzer cartridge is a safe procedure for the patient. While studies suggest that there is no risk of thromboembolic complications should this occur, complete clotting of the dialyzer circuit could result in up to ~228 mL of blood loss, and is usually prevented by replacing the dialyzer before complete occlusion.

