8. Surgery within the past 90 days prior to dosing which in the opinion of the PI or designee is clinically relevant.
9. Currently have established underlying inherited or acquired symptomatic bleeding disorders and/or are at risk for excessive bleeding per PI judgment or current active bleeding (e.g., gastrointestinal, intracranial), aside from minor bleeding from the puncture site on the AV fistula or AV graft, which would be expected to occur during the dialysis procedure, with the following values:
 - Platelet count < 100,000 cells/mm³ (if < 100,000 cells/mm³ but > 75,000 cells/mm³, with permission of PI and medical monitor) at screening or check-in on Day -8
 - INR > 1.4 at screening or check-in on Day -8
 - aPTT up to 1.2 x upper limit of normal (ULN) (if > 1.2 x ULN and up to < 1.5 x ULN, with permission of PI and medical monitor) at screening or check-in on Day -8
 - Alanine aminotransferase (ALT) or aspartate aminotransferase (AST) > 2 x ULN at screening or check-in on Day -8
 - Total bilirubin > 1.2 x ULN at screening or check-in on Day -8
10. Seated blood pressure < 90/40 mmHg at screening and check-in on Day -8.
11. Exclusion criteria for ECG at screening and check-in on Day -8:

Heart rate	< 45 and > 110 bpm
QTcF interval	> 500 msec
bpm = beats per minute; msec = milliseconds; QTcF = QT interval corrected using Fridericia's formula	

- Any significant arrhythmia or conduction abnormality, (including but not specific to atrioventricular block [2nd degree or higher], Wolff Parkinson White syndrome [unless curative radio ablation therapy]), which, in the opinion of the PI and Medical Monitor, could interfere with the safety for the individual patient.
- Non-sustained or sustained ventricular tachycardia (> 2 consecutive ventricular ectopic beats at a rate of > 1.7/second).

12. History of a CS allergy or a known sensitivity or idiosyncratic reaction to any compound known to be present in E-WE thrombin, its related compounds, or any compound listed as being present in the study formulation.
13. Hypersensitivity to β -lactam / penicillin derivatives.
14. Participate in strenuous exercise from 72 hours prior to check-in on Day -8 and throughout the study.
15. Positive test for drugs of abuse and/or positive alcohol test at screening or check-in on Day -8 if not accounted for by a prescription medication. Patients with a positive test based on a prescribed medication may be enrolled.

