14.3 Safety Data Summary Tables

14.3.1 Displays of Adverse Events

Table 14.3.1.1 Treatment-emergent Adverse Event Frequency by Treatment – Number of Subjects Reporting the Event (% of Subject Dosed) (Safety Population)

Table 14.3.1.2 Treatment-emergent Adverse Event Frequency by Treatment – Number of Adverse Events (% of Total Adverse Events) (Safety Population)

Table 14.3.1.3 Treatment-emergent Adverse Event Frequency by Treatment, Severity, and Relationship to Drug – Number of Adverse Events (Safety Population)

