 If a subject has 2 or more clinical adverse events, the subject is counted only once within a category. The same subject may appear in different categories.

Program: /CAXXXX/sas_prg/stsas/tab_PROGRAMNAME.sas DDMMYYYY HH:MM

Table 14.3.1.2 Treatment-Emergent Adverse Event Frequency by Treatment – Number of Adverse Events
 (% of Total Adverse Events) (Safety Population)

Adverse Event*	Dose Level of E-WE Thrombin			
	1.5 µg/kg	3.0 µg/kg	Placebo (Pooled)	Overall
Number of TEAEs	X (100%)	X (100%)	X (XX%)	X (XX%)
Nervous system disorders	X (XX%)	X (XX%)	X (XX%)	X (XX%)
Dizziness	X (XX%)	X (XX%)	X (XX%)	X (XX%)
Headache	X (XX%)	X (XX%)	X (XX%)	X (XX%)
Presyncope	X (XX%)	X (XX%)	X (XX%)	X (XX%)
Respiratory, thoracic and mediastinal disorders	X (XX%)	X (XX%)	X (XX%)	X (XX%)
Dry throat	X (XX%)	X (XX%)	X (XX%)	X (XX%)
Oropharyngeal pain	X (XX%)	X (XX%)	X (XX%)	X (XX%)
Sinus congestion	X (XX%)	X (XX%)	X (XX%)	X (XX%)
Sneezing	X (XX%)	X (XX%)	X (XX%)	X (XX%)
General disorders and administration site conditions	X (XX%)	X (XX%)	X (XX%)	X (XX%)
Fatigue	X (XX%)	X (XX%)	X (XX%)	X (XX%)
Thirst	X (XX%)	X (XX%)	X (XX%)	X (XX%)

Note: *Adverse events are classified according to MedDRA Version 21.1. ^ = Treatment-emergent adverse events

Program: /CAXXXX/sas_prg/stsas/tab_PROGRAMNAME.sas DDMMMYYYY HH:MM

Table 14.3.1.3 Treatment-Emergent Adverse Event Frequency by Treatment, Severity, and Relationship to Study Drug – Number of Adverse Events (Safety Population)

Adverse Event*	Cohort/ Treatment	Number of Subjects With TEAEs	Number of TEAEs	Severity				Relationship to Study Drug			
				Grade 1	Grade 2	Grade 3	Grade 4	Unrelated	Unlikely	Possibly	Probably
Dizziness	1/A	X	X	X	X	X	X	X	X	X	X
	X/X	X	X	X	X	X	X	X	X	X	X
Dry eye	X/X	X	X	X	X	X	X	X	X	X	X
Dry mouth	X/X	X	X	X	X	X	X	X	X	X	X
Dry throat	X/X	X	X	X	X	X	X	X	X	X	X
Ear pain	X/X	X	X	X	X	X	X	X	X	X	X
Fatigue	X/X	X	X	X	X	X	X	X	X	X	X
Headache	X/X	X	X	X	X	X	X	X	X	X	X
Dizziness	X/X	X	X	X	X	X	X	X	X	X	X
Hyperhidrosis	X/X	X	X	X	X	X	X	X	X	X	X
Laceration	X/X	X	X	X	X	X	X	X	X	X	X
Limb crushing injury	X/X	X	X	X	X	X	X	X	X	X	X
Muscle twitching	X/X	X	X	X	X	X	X	X	X	X	X
1.5 µg/kg E-WE Thrombin	X	X	X	X	X	X	X	X	X	X	X
3.0 µg/kg E-WE Thrombin	X	X	X	X	X	X	X	X	X	X	X
Placebo (Pooled)	X	X	X	X	X	X	X	X	X	X	X
Overall	XX	XX	X	X	X	X	X	X	X	X	X

Note: Treatment: A = 0.5 µg/kg bolus dose of E-WE Thrombin followed by a 0.25 µg/kg/hour continuous infusion over 4 hours for a total dose of 1.5 µg/kg

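### The planned TEAE tables give no by-treatment count of patients with any bleeding or any thrombotic event, and the SAP drops the protocol's access-site bleeding incidence

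*SAP*

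**What the plan says.** SAP 7.3 sets the level of tabulation: "TEAEs will be tabulated by System Organ Class (SOC) and Preferred Term". It also sets the statistic: "Summary tables will include number of subjects reporting the AE and as percent of number of subjects dosed by treatment and overall". SAP 9.2 then lists three TEAE tables. Table 14.3.1.1 counts subjects and Table 14.3.1.2 counts events, both in SOC and preferred-term rows. The third, 14.3.1.3, is "Treatment-emergent Adverse Event Frequency by Treatment, Severity, and Relationship to Drug"; its shell has preferred-term rows only. An SAE listing follows. The shell footnote to 14.3.1.1 says a subject is counted once within a category but adds: "The same subject may appear in different categories".

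Neither document defines an adverse event of special interest, a term list or a composite for bleeding or for thrombosis.

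The protocol treats hemostasis as an open matter. Section 8.4 says: "The hemostatic safety of E-WE thrombin in the complex conditions of ESRD and chronic HD is not yet known". Section 8.3.1 says: "Both thromboembolism and bleeding are common comorbidities in ESRD patients on HD". Safety and tolerability is the primary objective (protocol 9.1).

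On the access site, protocol 14.3.1 promises that both the incidence and the time of bleeding will be counted, and that active treatment will be compared with pre-treatment, placebo and post-treatment. SAP 7.11 and Table 14.3.5.9 give only summary statistics for time to clot. SAP 8 reports no departure from the protocol's analyses.

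**The concern.** For an antithrombotic, a clinical reader will first ask how many patients on each dose had any bleed, and how many had any thrombotic event, compared with placebo. Both kinds of event are common background in hemodialysis patients, so the placebo comparison is what makes them interpretable. The planned tables do not answer that question.

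The protocol's own examples cross organ systems. They include gastrointestinal and intracranial bleeding (exclusion 9), coronary, cerebral and venous thrombosis (exclusion 1), and occlusion of the fistula or graft (13.2.5). In the first-in-human study the one bleeding TEAE was at a puncture site (8.2.2.1). In tables organised by organ class and preferred term, such events would be expected to land in different rows.

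A patient count could be rebuilt later from the by-subject listings. But those listings show treatment, and no list of qualifying terms exists. The terms would then be chosen with the allocation in view, on a question that belongs to the primary objective. SAP 1 treats analyses outside the plan as out of scope, to be described in the study report.

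**Working it through.** There is no planned figure to reproduce. Protocol 14.1 says the sample size was chosen without statistical considerations and gives no event rate. The check is therefore a reading of the displays, followed by illustrations.

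**Inputs.** Protocol 14.1: two cohorts of 18 at 2:1, so 12 patients on each dose and 2 × 6 = 12 on placebo, pooled under protocol 14.3.1. Event counts and rates below are assumed.

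**1. Does any planned display give the count?**

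| Display | What it gives | Patients with any bleed or any thrombosis, by treatment? |
|---|---|---|
| Table 14.3.1.1 | Subjects per SOC and preferred term | No |
| Table 14.3.1.2 | Events per SOC and preferred term | No |
| Table 14.3.1.3 | Preferred term by severity and relationship | No |
| Table 14.3.5.9 | Bleeding time, continuous, access site only | No |
| Table 14.3.5.5 | Coagulation and platelets, fold change | No, laboratory values |
| Appendix 16.2.8.4 | Access-site reactions, listed | No |
| Tables 14.2.2.1 and 14.2.3.1 | Circuit clotting grade by treatment and day | No, device efficacy |

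**2. Can rows be added?** No. If k rows in a group of n show counts r₁ to r_k, the number of distinct patients lies between max(r) and min(n, Σr). Three rows of 1/12 are compatible with 1 to 3 patients, that is 1/12 = 8% to 3/12 = 25%.

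**3. Precision (Clopper-Pearson 95%, n = 12).**
- One row, 1/12: 0.2% to 38.5%.
- Pooled, 3/12: 5.5% to 57.2%.
- No events, 0/12: upper limit 1 − 0.025^(1/12) = 26.5%.

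For 3/12 against 0/12, the Newcombe interval uses Wilson limits of 8.9% to 53.2% and 0% to 24.2%.
- Lower: 25 − √[(25 − 8.9)² + 24.2²] = −4.1 points.
- Upper: 25 + (53.2 − 25) = 53.2 points.

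**4. Visibility.** Assume four bleeding terms, each with a 5% patient rate, independent.
- One given row shows at least two patients with probability 1 − 0.95¹² − 12 × 0.05 × 0.95¹¹ = 11.8%.
- At least one of the four rows does so with probability 1 − (1 − 0.118)⁴ ≈ 40%.
- The pooled rate is 1 − 0.95⁴ = 18.5%, and the pooled row shows at least two patients with probability 68.2%.

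At 2% per term the single-row and pooled figures are 2.3% and 23.8%; at 8% they are 24.9% and 89.5%. Pooling makes scattered events easier to see, by an amount that depends on these assumptions.

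**5. Access-site bleeding.** Protocol 14.3.1 names two quantities, incidence and time. The Table 14.3.5.9 shell shows n, mean, SD, minimum, median and maximum of a time. The incidence has no table, and SAP 8 does not record its removal.

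**The case against.** The strongest reply is that hemostatic safety is already covered. Bleeding time is summarised by treatment at five sessions, three of them before dosing. Coagulation tests and platelets are summarised before and after dialysis by treatment. New access-site findings are reported as adverse events, and protocol 8.4 names such measures as the safety monitoring. This stands, and it rules out a stronger reading that a reader might infer: that the trial reports nothing by treatment on bleeding risk. What these outputs lack is the patient count.

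A second reply is that the AE tables are better than a quick reading suggests. SOC rows already count a patient once within a class, and 14.3.1.3 gives severity and relationship for each preferred term. That is correct. But a SOC row also holds events that are not bleeds, and nothing removes duplicates across classes.

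Third, a reader might infer that the trial was run to estimate a bleeding incidence. No document says so. The primary outcome is general safety, and the words "without clinically significant impairment of the patient's hemostasis or promoting thrombosis" in protocol 8.3.1 describe what the drug is expected to do, not an endpoint.

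Fourth, with about 36 patients a de-duplicated count from Appendix 16.2.7.2 is quick work. This is true, so the claim that scattered events would go unnoticed is too strong. The remaining problem is that the terms would be chosen late.

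Finally, an undifferentiated any-bleeding row would mix minor puncture-site bleeding, which exclusion 9 treats as expected during dialysis, with serious bleeding. This is a fair criticism of a simple pooled row, and the table proposed below separates the two.

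**Conclusion.** The point holds as a reporting gap. No planned display gives the number of patients with any bleeding TEAE or any thrombotic or embolic TEAE by treatment, and the planned rows cannot be summed to obtain it. Separately, the SAP omits the access-site bleeding incidence that the protocol promises, while declaring itself aligned.

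The consequence is moderate. The study is descriptive, so sample size and error rates are untouched. A pooled row would not settle the safety question either: in the illustration of 3/12 against 0/12 the difference still spans zero (−4.1 to 53.2 points), and 0/12 leaves rates up to 26.5% compatible with the data. Its value is an honest patient count, with its uncertainty, on terms fixed in advance.

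The finding of a gap rests on the documents alone. The size illustrations rest on assumed counts, and the visibility figures also on equal, independent rates. How events would scatter is inferred from the organ systems the protocol names, not from any coding rule given in the documents.

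**What to change.** In SAP 7.3 and 9.2, add one table to the 14.3.1 group:
- Patients with at least one bleeding TEAE, with puncture-site bleeding and other bleeding in separate rows.
- Patients with at least one thrombotic or embolic TEAE, including access thrombosis.
- Columns for each dose, all active and pooled placebo.
- n (%) with exact 95% confidence intervals labelled as descriptive, and a split by severity grade.

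Attach both preferred-term lists to the SAP. Fix them in a blinded review of the coded terms before unblinding.

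In SAP 7.11, restore the access-site bleeding incidence by treatment and session, with the comparisons that protocol 14.3.1 promises. State how incidence is defined from the recorded checks. If the sponsor prefers to drop it, SAP 8 should record the change and the reason.

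The cost is one new table, one added display for access-site incidence and a short blinded term review, with no new data or visits. The intervals will be wide at 12 per group, and the text should say so.
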